13.5 Single IRB

Johns Hopkins Medicine is serving as the single IRB for this study. It is the preference of Johns Hopkins Medicine IRB to use the SMART IRB reliance agreement as the basis of reliance. The

SMART IRB master reliance agreement was created in 2016 to harmonize and streamline the IRB review process for multisite studies. It enables reliance on a study-by-study basis, clearly defines roles and responsibilities of relying institutions and reviewing IRBs, and eliminates the need to sign reliance agreements for each study [e.g., a non-SMART IRB agreement]. 900+ institutions have already signed onto this agreement and are actively using it as the basis of reliance for multisite projects. Sites that will rely on JHM IRB are still responsible for conducting a local context review prior to the start of research at their site and for following any local and institutionally required policies as it applies to research at their site [e.g., reporting of unanticipated problems].

13.6 Study organization

Study organization will be based directly on the existing organizational framework used in the ongoing ACHIEVE trial consisting of an overarching Steering Committee that interfaces with the ARIC study, NIH, and DSMB (when applicable). Under the Steering Committee, several additional committees (Operations, Quality Control, Neurocognitive Adjudication, Intervention Fidelity and Quality, and Publications) oversee day-to-day execution of the study.

14 History of protocol amendments

Minor changes to page numbering and formatting and minor corrections and clarifications were made throughout the document. Substantive changes are highlighted in the below table.

Protocol version	Affected section(s)	Brief description of change	Brief rationale for change
v1.0 (29-Jun-2021)	Original version of th	e protocol approved by the sIR	RB.
v1.1	Version of the protoc	ol approved at the time the firs	t participant was randomized.
(20-Sep-2021)	5.1 Eligibility	Vision impairment exclusion criteria changed from 20/40 to 20/63	This is a correction to match the criteria used in ACHIEVE
	7.1 Schedule of activities (Table 1);	Telehealth Sessions renamed from Session 1, 2,	Sessions named with letters, rather than numbers, is consistent with
	9.2 Telehealth hearing health care;	3 to Session A, B, C	how intervention sessions have been named previously in ACHIEVE
	9.3.1 Crossover to telehealth HHC delivery model		
	7.1 Schedule of activities (Table 1)	Visits renamed as follows: Yr 0.5→ 6-month Yr 1→ Year 1 Yr 1.5→ 18-month Yr 2 → Year 2	Consistency with visit names used in the database

Protocol version	Affected section(s)	Brief description of change	Brief rationale for change
version	7.1 Schedule of activities (Table 1); 9.1 Interventions – all participants; 9.3 Conventional clinic-based hearing health care	HIFU Intervention check-up added to Randomization Visit and noted as only required at Session A if not the same day as the visit	HIFU Intervention check-up should be done on all participants at the start of HIFU; HIFU Intervention check-up should be repeated during Session A if Session A occurs on a separate day from Randomization/Year 1 Visit; otherwise, it should not be repeated
	7.1 Schedule of activities (Table 1); 7.5.5 COVID impact questionnaire	Added COVID impact questionnaire to semi-annual and annual visits	This questionnaire, which was added during the ACHIEVE parent trial, and which we had planned to continue administering it in ACHIEVE-HIFU, had been inadvertently omitted from the protocol
	7.1 Schedule of activities (Table 1); 7.5.6 Telehealth acceptance questionnaires	"Telehealth acceptability" changed to "Telehealth acceptance"	Correction
	7.1 Schedule of activities (Table 1); 9.1 Interventions – all participants; 9.2.1 Telehealth session A	Telehealth acceptance questionnaires moved out of Session A to the Randomization/Year 1 Visit	TAP should be collected on all participants at Randomization, and ideally, should be collected by a non-audiologist. At the Year 1 Visit, a non-audiologist should administer the TAP or TAF, depending on whether the participant has received the telehealth intervention yet.
	7.1 Schedule of activities (Table 1);	CDP, CDI, CDS, and NPI removed from semi-annual visits.	This is a correction for consistency with what is currently being done in ACHIEVE.
v1.2 (20-Jan-2022)	Cover page	Clinicaltrials.gov identifier added.	The Clinicaltrials.gov registration was completed prior to enrollment of participants, and the protocol is being updated to reflect the identifier.
	3 Study objectives and end points	Details on how outcomes are assessed and scored, and interpretation of scores have been added.	Descriptions of the outcomes were expanded to clarify the outcomes and make them consistent with the outcomes listed in the study's clinicaltrials.gov record.
	6.1 Informed consent	Added sub-section on re- obtaining consent in the event of consent changes.	The protocol did not previously address the process for re-consent due to consent changes. Because the study involves telehealth (remote) visits, and not all contacts occur in person, flexibility has been added to allow re-consent to be provided verbally or via mail.

Protocol	Affected section(s)	Brief description of change	Brief rationale for change
version			
	6.2 Participant confidentiality	Details on the results provided to participants and their private physicians were updated.	These changes reflect corrections to the planned sharing of results to correspond with sharing of results in the parent ACHIEVE trial.
	7 Study assessments and procedures	Removed the stipulation that the parent ACHIEVE trial Year 3 visit will serve as the baseline if completed within the 6 months preceding randomization in ACHIEVE- HIFU.	Decision by the ACHIEVE investigators to allow the Year 3 ACHIEVE visit to serve as the baseline for ACHIEVE-HIFU, even if more than 6 months have passed, and to not conduct a repeat baseline visit. This change allows additional scheduling flexibility and reduces potential participant burden.
	7.1 Schedule of activities (Table 1)	COSI goals achievement removed from the Initial Conventional Randomized HHC arm's Telehealth Session A.	This removal is a correction – goals achievement will be assessed at the Year 1 visit, which will often occur the same day or within the week prior to Session A for the group randomized to conventional HHC, so goals achievement will not be repeated at Session A.
	12 Data management	Removed text indicating that technicians will be blinded to randomization status.	The primary outcome for ACHIEVE-HIFU is objectively measured hours of hearing aid use, so technicians collecting other outcomes are not required to be blinded.
	14 History of protocol amendments	New section added.	The relevant summary of changes for the current protocol version will be outlined in the table at the beginning of the protocol, but the full history of protocol changes will be maintained within this newly added section in the protocol.

15 References

- 1. American Speech-Language Hearing Association (ASHA). *Preferred Practice Patterns for the Profession of Audiology*. Rockville, MD; 2006.
- 2. Audiology Australia. *Audiology Australia Professional Practice Standards Part B: Clinical Standardsle*. Forest Hill, Victoria; 2013.

The Aging & Cognitive Health Evaluation in Elders (ACHIEVE) Hearing Intervention Follow-Up (HIFU) study is a randomized controlled trial nested within the ACHIEVE trial. Approximately 340 of the 490 participants in the hearing intervention group from the parent ACHIEVE study will be randomized to one of two conditions—telehealth Hearing Health Care (HHC) or conventional HHC. ACHIEVE-HIFU participants will be community-dwelling adults that were assigned to the hearing intervention arm of ACHIEVE, completed their final ACHIEVE Year 3 visit, and are willing and able to participate in two additional years of follow-up.

2. Background

Age-related hearing loss in older adults is a chronic health condition, according to the World Health Organization [1] [2] [3]. Current rates of hearing aid use among older adults with hearing loss in the U.S. are <20%, and rates of discontinuation of hearing aid use among older adults are estimated to be >30% [4] [5] [6] [7]. The clinic-based HHC model may be a contributor to low hearing aid utilization rates [8] [9] [10] [11]. Telehealth delivery of HHC is a form of remote service delivery that allows patients to access health care services from home via smartphones, tablets, and computers. Telehealth can be used to deliver services to adults with hearing loss including ongoing self-management support [12].

3. Objectives

The primary aim of ACHIEVE-HIFU is to compare the effect of telehealth HHC vs conventional HHC on hours of hearing aid use at one-year post-randomization. A secondary aim is to examine the effects of telehealth HHC vs conventional HHC on patient-centered hearing and communication outcomes. Exploratory analyses include (1) subgroup analyses of the primary and secondary outcomes, (2) differences in the utilization of hearing services, (3) quantifying the dose-response relationship between utilization of hearing services and hours of hearing aid use, and (4) assessing trends over time from randomization to the two-year follow-up.

4. Study Design

ACHIEVE-HIFU is a randomized trial with two treatment arms: telehealth HHC and conventional HHC. Both treatment arms will receive the same clinic-based hearing intervention provided in the parent ACHIEVE study. However, participants assigned to the telehealth HHC treatment arm will be granted immediate access to HHC services via telehealth. Participants assigned to the conventional HHC treatment arm will be given access to the same telehealth services one year after randomization.

To be eligible for ACHIEVE-HIFU, participants must (1) have been eligible for and participated in the hearing intervention arm of ACHIEVE, (2) complied with ACHIEVE protocols, (3) be willing to be randomized to the telehealth HHC or conventional HHC treatment arm, and (4) be willing and able to complete two years of follow-up. The inclusion criteria for ACHIEVE were (1) 70 to 84 years old, (2) adult-onset bilateral hearing loss with a better-ear 4-frequency (0.5 to 4 kHz) pure tone average ≥ 30 and <70 dB, (3) free of substantial cognitive impairment (Mini-Mental State Exam ≥ 23 for high school degree or less; ≥ 25 for some college or more), (4) word recognition score in quiet $\geq 60\%$ correct in the better-hearing ear, community-dwelling, and (5) being a fluent English speaker. The exclusion criteria for ACHIEVE were (1) self-reported disability in ≥ 2 activities of daily living, (2) vision impairment worse than 20/63 on the MNREAD acuity chart (Precision Vision, Woodstock, IL) while using glasses or other reading aids typically used at home (corresponding to inability to comfortably read 14-point font), (3) self-reported hearing aid use in the past year, (4) permanent conductive hearing loss, (5) medical contraindication to hearing aid use, or (6) unwillingness to wear hearing aids on a regular basis.

Randomization for ACHIEVE-HIFU occurred up to 9 months after the participant's ACHIEVE Year 3 visit except at the University of Minnesota where delayed Institutional Review Board approval caused some participants to be randomized after more than 9 months. Spouse pairs were randomized to the same treatment arm. Participants will be followed for two years, with ACHIEVE Year 3 visit serving as the baseline.

5. Power

ACHIEVE-HIFU is predicated on a finite sample of participants recruited from the treatment arm of the parent ACHIEVE study. An estimated 340 participants will be randomized to telehealth HHC or conventional HHC. Assuming conservatively that 5% of participants are lost to follow-up or death each year, we would have a sample of N=322 participants one-year post-randomization. With 80% power and a 5% Type 1 error rate, this sample would have the ability to detect an average treatment effect of 1.5 hours of hearing aid use between the telehealth HHC and conventional HHC arms.

6. Analysis Populations

Analyses will follow the intention-to-treat (ITT) principle in which participants will be analyzed in the condition to which they were randomized, regardless of whether they received the assigned intervention. Primary analyses will be based on the ITT population, which includes all randomized participants.

7. Statistical Analysis

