11.1 Sample size

This study is predicated on an already established cohort with a fixed sample size from the original ACHIEVE trial (N=490 for the clinic-based hearing intervention cohort). In order to estimate the minimal difference in hours of continued hearing aid use that could be detected between the telehealth and conventional HHC groups after 12 months, we've made conservative assumptions based on expected loss to follow-up over time that would diminish the sample size and any observable outcomes. The initial cohort receiving the hearing intervention was N=490. Assuming conservatively that 5% of participants per year in this cohort are lost to follow-up or death, we would have a potential cohort of N=420 participants who would be eligible to participate after 3 years of follow-up from 2021-2022. If we further assume that up to 5% of these participants may then decline additional follow-up, we conservatively estimate that N=400 participants currently in the hearing intervention group will be recruited into this follow-up study (ACHIEVE-HIFU). Further conservatively assuming: 1) 10-20% loss to follow-up in the 12-month follow-up data collection; 2) 80% power and a 5% Type 1 error rate; and 3) that patterns of hearing aid utilization will be similar to those observed in the ACHIEVE pilot study, we would have the ability to detect an average treatment effect of 0.8 to 0.9 hours of hearing aid use between the telehealth HHC and conventional HHC arms.

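### SAP section 5 sets its analysed N and detectable difference on 5% one-year loss, where the protocol assumes 10-20% for the same visit, with no reason given

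*SAP*

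**What the plan says.** **SAP.** The opening section expects "Approximately 340 of the 490 participants in the hearing intervention group" of the parent trial to be randomised. Section 5 repeats this ("An estimated 340 participants will be randomized to telehealth HHC or conventional HHC") and continues: "Assuming conservatively that 5% of participants are lost to follow-up or death each year, we would have a sample of N=322 participants" at one year. For that sample, at 80% power and 5% type 1 error, the detectable difference is given as "an average treatment effect of 1.5 hours of hearing aid use between the telehealth HHC and conventional HHC arms". No SD is given, and the text does not say whether the test is one- or two-sided.

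**Protocol 11.1.** The protocol uses three separate loss steps:

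- 5% per year over three years of the parent trial, taking 490 to 420.
- Up to 5% declining further follow-up, so that "we conservatively estimate that N=400 participants currently in the hearing intervention group will be recruited".
- On top of these, for the primary-outcome visit, "10-20% loss to follow-up in the 12-month follow-up data collection".

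With 80% power and 5% type 1 error it then claims to "detect an average treatment effect of 0.8 to 0.9 hours of hearing aid use". It refers to usage patterns in the ACHIEVE pilot but gives no SD.

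**The concern.** In the protocol, 5% per year is the rate for carrying the parent cohort forward to the start of this study. Loss at the 12-month outcome is a different and larger allowance. The SAP applies the 5% to the outcome visit, omits the 10-20% and gives no reason. A rate below the protocol's own range cannot be called conservative without evidence.

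The SAP also counts only loss to follow-up and death. Protocol 7.2.1 restricts reading of the hearing aid data log to in-person visits, while Protocol 7.1 and 5.2 allow visits by telephone or video. A participant can therefore stay in the study and still have no primary outcome. The documents give no figure for this, but it can only add to the missing data.

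At stake is the planning statement for the primary outcome. If fewer than 322 participants supply log data, a null result may be judged against a sensitivity that the trial did not reach.

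**Working it through.** **Inputs.** 340 randomised, 5% loss, N = 322, 1.5 h, 80% power and 5% type 1 error (SAP section 5); 10-20% loss and 0.8 to 0.9 h (Protocol 11.1); 1:1 allocation (Protocol section 8). Assumed: two-sided test and normal approximation, so z = 1.960 + 0.842 = 2.802. Spouse-pair clustering, covariate adjustment and weighting are ignored, because the documents give no figures for them.

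**1. The plan's own counts.**
- Protocol: 490 × 0.95³ = 420; 420 × 0.95 = 399, stated as 400. Reproduced.
- SAP: 340 × 0.95 = 323, or 161.5 per arm; 161 × 2 = 322. Reproduced.

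**2. The SAP's power figure.** It cannot be reproduced without an SD. Solving for the SD that makes it true:

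SD = 1.5 × √(322/4) / 2.802 = 4.80 h.

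If 1.5 is rounded from 1.45 to 1.55, the implied SD is 4.64 to 4.96 h.

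**3. The SD implied by the protocol.** N = 400 less 10-20% is 360 to 320.
- 0.8 × √(360/4) / 2.802 = 2.71 h
- 0.9 × √(320/4) / 2.802 = 2.87 h

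The implied SD therefore rises from about 2.7-2.9 h to 4.8 h between the documents, unexplained. At the protocol-implied SD, N = 322 would detect about 0.85 to 0.90 h, so the smaller sample does not account for the move to 1.5 h.

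**4. Protocol loss applied to the SAP's 340.** 340 × 0.90 = 306; 340 × 0.80 = 272.

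**5. Effect on precision.** Detectable difference at 80% power = 2.802 × 2 × SD / √N. Power for 1.5 h = Φ(1.5 × √N / (2 × SD) − 1.960). Each cell gives power for 1.5 h, then the detectable difference.

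| SD (h) | N = 322 (SAP) | N = 306 (10% loss) | N = 272 (20% loss) |
|---|---|---|---|
| 2.71 (implied by protocol) | 99.9%; 0.85 h | 99.8%; 0.87 h | 99.5%; 0.92 h |
| 2.87 (implied by protocol) | 99.7%; 0.90 h | 99.5%; 0.92 h | 99.0%; 0.98 h |
| 4.0 | 92.0%; 1.25 h | 90.7%; 1.28 h | 87.1%; 1.36 h |
| 4.5 | 84.9%; 1.41 h | 83.0%; 1.44 h | 78.5%; 1.53 h |
| 4.80 (implied by SAP) | 80.0%; 1.50 h | 78.0%; 1.54 h | 73.1%; 1.63 h |
| 5.0 | 76.8%; 1.56 h | 74.7%; 1.60 h | 69.6%; 1.70 h |

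The SD at which N = 272 still gives exactly 80% power for 1.5 h is 1.5 × √272 / (2 × 2.802) = 4.41 h.

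**The case against.** **The power at N = 322 is untouched.** Attrition decides whether 322 is reached, not what 322 can detect. A reader might infer that the 80% claim at N = 322 is false. The documents do not support that: without a stated SD it can be neither confirmed nor refuted, and the 4.80 h used above comes from assuming the claim is true. This stands. The point is confined to the N that the plan can expect and the difference that goes with it.

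**The effect is small and conditional.** On the implied SD, the detectable difference grows by 0.04 to 0.13 h, about 2 to 8 minutes a day. At 10% loss, 1.54 h still rounds to 1.5 h. At an SD of 4.0 h, power exceeds 80% throughout. This also stands; the figures belong in a range.

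**The fall from 400 to 340.** A reader might take this as proof that 5% per year was too low. It is not. The 400 already includes a refusal step. SAP section 4 lists compliance with the parent trial's protocols as an eligibility condition, which Protocol 5.1 does not. The 340 is itself an estimate. Parent attrition of exactly 5% a year would leave 420, and 1 − 340/420 = 19% refusal or ineligibility would then give 340. The documents do not separate these causes.

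**No analysis changes.** The cohort is fixed, Protocol 10.1 plans no interim look for efficacy or futility, and SAP 7.3 reports bootstrap intervals with attrition weights from the data obtained. That limits the consequence, but it does not reconcile two loss assumptions for one visit.

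**Conclusion.** The point holds as an unexplained conflict between the SAP and the protocol on the loss rate that sets the analysed N for the primary outcome. On the protocol's assumption, the SAP's 340 yields 306 to 272 participants, which is 16 to 50 fewer than stated.

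The cost in precision depends on an SD that neither document gives. At the SAP-implied 4.80 h (two-sided 5%, 1:1), the detectable difference is about 1.54 to 1.63 h and power for 1.5 h about 78% to 73%. That is negligible at the lower end of the loss range and visible at the upper end. At an SD of about 4.0 h or less, power for 1.5 h stays above 80% even at 20% loss.

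A reader might also see the step from 323 to 322 as a calculation error. It is consistent with rounding to equal whole arms, and the difference is immaterial. The sums are right; the assumptions disagree.

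**What to change.** In SAP section 5:

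1. Delete the word conservatively.
2. Reconcile 5% with the protocol's 10-20%. Alternatively, justify 5% with the observed availability of data-log outcomes at the equivalent parent-trial visit, counting retained participants without a log reading as missing.
3. State the SD used, its source and whether the test is two-sided. This would also let a reader see why the detectable difference moved from 0.8-0.9 h to 1.5 h.
4. Report the analysed N and the detectable difference over N = 272 to 322 with that SD. If it is 4.80 h, the range is about 1.5 to 1.63 h. The 4.80 h should not be written in unless it has a source, because here it is only back-solved.

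The cost is a few lines of SAP text and a slightly less favourable stated figure. No extra enrolment is required, and the primary analysis does not change.

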7.1 General Considerations

Study data will be monitored on an ongoing basis by the Data Coordinating Center (DCC). The DCC will send data clarification requests to the clinical sites for resolution while the study is ongoing. Final cleaning and editing of the study database will be carried out after the final participant completes their one-year follow-up assessment. The process will be repeated after the final participant completes their two-year follow-up assessment. Unblinding of treatment assignments will not be performed until the study data are cleaned, queries resolved, and database lock achieved. A permanent archive of the database will be maintained by the DCC. Randomization will be implemented within the Carolina Data Acquisition and Reporting Tool used by the DCC. Although the ACHIEVE hearing interventions are by nature unmasked, in order to minimize bias based on review of accumulating data by the project team, the ACHIEVE PIs, co-investigators, and key project staff (except one unblinded statistician) will remain blinded to accumulating data. In all cases, hours of hearing aid use (primary outcome), a completely objective data point, will be gathered directly from hearing aid data logging software, and source data will be verified as part of the quality assurance procedures. All other non-audiological secondary outcomes will be collected by trained technicians, rather than the site audiologist.

This statistical analysis plan (SAP) was developed prior to review of the study dataset and under the assumption that all data were collected in adherence to the protocol and in accordance with good clinical research practices. As the data are analyzed, some deviation is anticipated (e.g., missing data, small sample sizes, etc.). In instances where these deviations would make the proposed analyses inappropriate, modifications to the analysis plan will be made and noted in the final report.

All programs used in the statistical analysis of study data will be documented, tested, and archived. This includes the original written specifications for the analyses, any subsequent modifications, the computer program file, and the log, list and other output files produced by the program. All programming will be done by the DCC using SAS® version 9 or later.

